## **3. METHODOLOGY**

Design: Multicentre randomized clinical trial

Reference population: Patients with a diagnosis of moderate-severe COPD treated with inhaled bronchodilators.

Study population: Patients with a diagnosis of moderate and / or severe COPD , with bronchodilator treatment in PC Centers, that meet the criteria for inclusion in the study.

Inclusion criteria: Patients who have been visited at least once last year at the center with diagnosis of COPD (J44), with a moderate airflow limitation (FEV1 between 50% - 80%) or severe airflow limitation(FEV1 between 30 % - 50%), treated with bronchodilators, and who accept to participate in the study.

Exclusion criteria

- Patients only receiving home attention (Z74)
- Patients with mental disorders and / or severe mental disorders that do not allow following the sessions
- Patients diagnosed with asthma, tuberculosis or other chronic respiratory diseases
- Patients receiving chronic home oxygen therapy (OCD).
- Patients with terminal disease.

Sample size and sample procedure: Accepting an alpha risk of 0.05 and a beta risk lower than 0.2 in a bilateral contrast, 182 subjects in the first group and 182 in the second are need to detect a difference equal to or greater than 3.51 Units in the St George's Respiratory Questionnaire. It is assumed that the common standard deviation is 11.33. A follow-up loss of 10% has been estimated. Patients will be contacted by phone, via sms, internet or at office consultation (according to the authorization given to the e-CAP) by offering participation in the study and a visit will be scheduled to explain the study and to obtain the signed informed consent and the collection of data.

The random distribution to the groups will be carried out centrally, through a computer program that generates the random numbers managed by a remote investigator to recruiters. The allocation of each patient will be hidden in an envelope that will be opened when the professional has confirmed that he complies with the selection criteria and the patient has signed the informed consent.

Variables

-Quality related to Health (QVRS) will be measured with specific and standardized self-administered questionnaires, validated by our environment:

- St. George's Respiratory Questionnaire (SGRQ) 22. It is divided into three subscales: symptoms (eight items), activity (16 items), and impacts (26 items). For each subscale and for the general questionnaire, the scores range from 0 (without deterioration) to 100 (maximum deterioration).

- COPD Assessment Test (CAT) 23. It consists of 8 questions with 5 possible answers valued from 0 to 5 (values close to 0: better health status)

-Pulmonary function: it will be measured with forced spirometry with a bronchodilatation test. According to a FEV1 / FVC ratio <70% and the FEV1 post bronchodilatation, patients will be classified in COPD: MILD FEV1> 80%; MODERATE: 50% - 80%; SEVERE: 30% -50%; VERY SEVERE: <30% 24.

-Dyspnea: Quantified by the modified scale of the Medical Research Council (mMRC) 25. It is part of the BODEx index (26).

-Pronostic: BODEx index (26). This index that can be scored from 1 to 3, depending on the variables: body mass index, FEV1, dyspnea (mMRC25 scale) and severe exacerbations of COPD.

-Anxiety and depression: they will be measured with the Goldberg's anxiety-depression scale (27).

-Hospital admissions in the last year (computerized medical history review).

Independent and confusing variables:

- Socio-demographic variables: age (date of birth), gender and level of studies.

-Date of diagnosis of COPD.

-Phenotype: non exacerbator; asthma- COPD; exacerbator with emphysema; exacerbator with chronic bronchitis (1).

Pharmacological treatment:

-Type of treatment: LABA, LAMA, LAMA + LABA, CI, SABA, SAMA, roflumilast.

-Pharmacological compliance: Assessed by the Morisky-Green test (28) that provides information about the causes of non-compliance. It consists of 4 questions with dichotomous response that must be introduced to the normal conversation with the patient.

Inhalation technique: practical test evaluating step by step the technique according to SEPAR and SEMFYC (29)

Comorbidities: hypertension, diabetes mellitus II, dyslipidaemia, depression and anxiety, joint disorders, cardiovascular disease, cardiovascular risk.

Tobacco: Not Smoker / Smoker / former smokers. Yes smoker or ex-smoker: no packages / year. If you smoke number of cigarettes / day. Nicotine dependence (Fargeström) (30), Motivation for change (Richmond) (31) and Phase of change (Prochaska and DiClemente) (32).

Alcohol: BU/week

Working exposure

Environmental exposure ambiental (contamination, tobacco...)

-Other variables:

-Degree of participation in the intervention: 1 session/ 2 sessions/ 3 sessions/ ≥ 4 sessions

All the variables studied will be collected at baseline, prior to the intervention, and at 6, 12 and 24 months later, both in the intervention and in the control groups.

The control group will follow the usual treatment and follow-up and a visit will be scheduled to obtain the same variables as the intervention group, on a first visit, and at 6, 12 and 24 months.

Collection of data and sources of information:

Data analysis: Analysis will be carried out by intention to treat basis. All patients who signed their informed consent and who have completed the initial evaluation will be included in the analysis. The descriptive statistics of dependent, confusing and general variables will be calculated, both for the intervention group and for the control group and the homogeneity of the two groups for these variables will be checked at the beginning of the study. In all cases, a bilateral alpha error of 0.05 will be considered and the confidence intervals will be calculated at 95%. A variable will be calculated for each

measurement time (baseline, 6 months post-intervention and 12 and 24 months), which is the difference between the result of SGRQ and the other dependent variables of interest in each cut and the initial value, for each individual. Differences between groups and the confidence intervals of the difference to 95% will be calculated. An analysis of the variance of repeated measures (ANOVA) will be performed to evaluate the differences in time of dependent variables attributable to the effect of the intervention. It will adjust for the possible confusers, comorbidity, other interventions carried out, among others.

Difficulties and limitations of the study: This is a clinical trial in which health professionals who usually see the subject of study can know the group to which the patient belongs. They will "try to preserve masking in some important stages of the study: random allocation, evaluation of the main measures, statistical analysis of the data. On the other hand, the duration of the study can lead to long term loss to follow-up. To ensure the patient's adherence telephone location will be performed (at least three attempts per appointment, if the patient has not indicated that he does not want to participate) when missing the intervention sessions and a quarterly reminder telephone contact.

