## **ABSTRACT**

**Background:** Chronic Obstructive Pulmonary Disease (COPD) is a problem of public health of great magnitude, increasing morbidity and mortality and of high cost both in health resource consumption and in loss of quality of life related to health (HRQL). The "comprehensive approach to this complex illness, promoting self-care, improves HRQL and the clinical situation of patients, as shown by several studies, but more studies are needed to corroborate these results in the " Primary Care Area " (PC), and to make clear recommendations about the most effective type of intervention.

**Hypothesis:** In patients with moderate to severe COPD, a self-care structured intervention is more effective than the usual intervention on the main variables associated with the disease: HRQL, pulmonary function, exacerbations, hospital admissions, in the setting of PC in a follow-up of 6, 12 and 24 months

**Objectives:** To evaluate the impact of a comprehensive intervention to promote self-care and improve HRQL in people with COPD in PC.

**Methods:** Randomized clinical trial multicentre with and control group, carried out at PC centers of Barcelona.

**Determinations:** specific questionnaires, standardized and validated, such as the St George's Respiratory for HRQL.

ifferences  
between groups and variance of repeated measures (ANOVA) will be used to evaluate the effect of the intervention.

**Expected results:** Significant improvement in HRQL in patients with COPD attributable to the intervention performed.

**Applicability and Relevance:** The intervention could be incorporated into regular clinical practice with standardized contents.

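### Allocation in a multicentre trial is described without balancing by centre or envelope safeguards, and centre is not a named covariate, although a remote investigator already manages the sequence and could release each assignment directly

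*Combined protocol and SAP*

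**What the plan says.** The trial is multicentre and, according to the Abstract, "carried out at PC centers of Barcelona". Individual patients are allocated. The sample size statement requires "182 subjects in the first group and 182 in the second are need".

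The randomisation method takes two sentences in section 3, Methodology (sample size and sample procedure). Allocation is "carried out centrally, through a computer program that generates the random numbers managed by a remote investigator to recruiters". Each patient's assignment is then hidden in an envelope, which is opened once the professional has confirmed the selection criteria and the patient has signed consent. The text does not say who opens the envelope, who holds it, or whether envelopes are sealed, opaque, numbered or logged. It mentions no strata, blocks or minimisation, and does not say whether there is one list or one per centre.

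Three other places bear on the point:

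- Data analysis: the repeated-measures ANOVA will adjust for possible confounders, comorbidity and other interventions. Centre is not named there or in the list of variables. The analysis set is patients who consented and completed the initial evaluation.
- Difficulties and limitations: the professionals who usually see the patient may know the group. Masking of the random allocation is an aim, but no procedure is given.
- Additional procedures: the programme is delivered locally, in visits with the reference nurse.

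**The concern.** Two things are left open that the existing set-up could settle.

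The first is concealment. A remote investigator already manages the sequence, so each assignment could be withheld until a patient is registered. The plan instead passes it through an envelope with no described control. Where staff are not blinded, an envelope opened early or out of order would allow selective enrolment, and later adjustment cannot fully remove that.

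A related gap is that opening depends on eligibility and consent, not on completion of the baseline evaluation, while the analysis set requires that evaluation. As written, a patient could be allocated, fail to complete baseline and leave the analysis after the arm is known.

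The second is centre. The reference nurse delivers the programme, so outcomes may well vary between centres. Centre is handled neither in the allocation as described nor by name in the model. Arms can then be uneven within centres by chance, and between-centre variation that could be removed stays in the error term.

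**Working it through.** **Inputs from the Methodology section.** "Accepting an alpha risk of 0.05 and a beta risk lower than 0.2 in a bilateral contrast"; target "a difference equal to or greater than 3.51 Units" on the SGRQ; "It is assumed that the common standard deviation is 11.33"; "A follow-up loss of 10% has been estimated". The number of centres, their sizes and the between-centre intraclass correlation (ICC) are not given, so these are assumed and varied.

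**1. Reproduce the plan's figure.** n per arm = 2 × [11.33 × (1.960 + 0.842) / 3.51]² = 163.6, or 164 evaluable. Dividing by 0.9 gives 163.56 / 0.9 = 181.7, so 182 per arm. The plan's figure reproduces.

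With 182 × 0.9 = 163.8 evaluable per arm, SE = 11.33 × √(2/163.8) = 1.252. Power = Φ(3.51/1.252 − 1.960) = Φ(0.844) = 80.1%.

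**2. Overall imbalance under simple randomisation.** The 95% range of a Binomial(364, 0.5) is 163 to 201. At 163:201 the evaluable numbers are 146.7 and 180.9. SE = 11.33 × √(1/146.7 + 1/180.9) = 1.259, and power = Φ(3.51/1.259 − 1.960) = 79.6%. The loss is about 0.4 points.

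**3. Imbalance within centres under simple randomisation.** For a centre of m patients, P = 2 × P(X ≥ k), where X ~ Binomial(m, 0.5) and k is 0.65m rounded up. Centres are assumed equal, with 364 patients in all.

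| Centres | m | k | P(65:35 or worse) | Expected number of such centres | P(at least one) |
|---|---|---|---|---|---|
| 5 | 73 | 48 | 1% | 0.05 | 5% |
| 10 | 36 | 24 | 7% | 0.65 | 49% |
| 20 | 18 | 12 | 24% | 4.8 | >99% |
| 30 | 12 | 8 | 39% | 11.6 | about 100% |

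**4. What this does to the SGRQ difference.** Centre effects with variance ICC × 11.33² contribute to the unadjusted difference a chance component with mean zero. Its SD is about 2 × 11.33 × √ICC × √(1 − 1/C) / √N, for C centres and N = 328 evaluable patients. For ICC 0.05 and C = 5: 2 × 11.33 × 0.2236 × 0.894 / 18.11 = 0.25 points.

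Simulation (20,000 runs per scenario, 5 to 30 centres) agrees:

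- ICC 0.01: 0.11 to 0.12 points
- ICC 0.05: 0.25 to 0.27 points
- ICC 0.10: 0.36 to 0.39 points

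The target difference is 3.51. If 11.33 is the total SD, this variance is already inside the SE of 1.252, so the 80.1% includes it.

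**5. Gain from balancing on centre and adjusting for it.** The residual SD becomes 11.33 × √(1 − ICC). Power = Φ(3.51 / [1.252 × √(1 − ICC)] − 1.960), which is 80.4% at ICC 0.01, 82.0% at 0.05 and 84.0% at 0.10.

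**The case against.** The strongest reply is that much of this rests on silence, and that the written procedure is sound where it speaks. Eligibility is confirmed and consent signed before the envelope is opened, which is a real safeguard. Change from baseline also removes stable differences between centres in SGRQ level, so the relevant ICC is that of change and may be small. The open-ended adjustment might include centre. Blocking within centre has its own cost: where staff can know the arm, assignments late in a block become partly predictable. All of this stands, and it limits the size of the point. It does not supply envelope safeguards, a stated method of balancing, or centre in the model.

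A reader might infer more, and the documents do not support it:

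- *That there is a single unrestricted list, so that centres are certainly unbalanced.* The text neither describes nor excludes lists or blocks by centre. It supports only the statement that none is described.
- *That recruiters hold the envelopes and the assessor of eligibility opens them.* The second is the natural reading, but no holder or opener is named.
- *That the exclusion of "Patients with mental disorders and / or severe mental disorders that do not allow following the sessions" will be applied differently by arm, because only the intervention arm has sessions.* In the written order this judgement precedes knowledge of the arm for every patient. Differential use would need a breach of that order.
- *That uneven centres bias the treatment effect.* Chance imbalance has mean zero and adds variance only.

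**Conclusion.** The point holds as a gap in specification with a cheap and better alternative. It does not show that the trial is biased or underpowered.

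Concealment is the stronger ground. The remaining risk is tampering or opening out of sequence, which no described control covers in a trial with unblinded staff. Its size cannot be calculated from the documents.

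The centre issue is smaller. Overall imbalance costs about 0.4 points of power at the edge of its 95% range. Within-centre imbalance is negligible with a few large centres and common with many small ones. Handling centre in both allocation and analysis would raise power from 80.1% to between 80.4% and 84.0%, which is useful because the plan has almost no reserve above 80%.

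These figures assume simple randomisation, equal centres, ICCs of 0.01 to 0.10, a total SD of 11.33 and 10% loss. If the sponsor already balances by centre, the allocation part reduces to stating it. Naming centre in the model and specifying concealment would still be needed.

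**What to change.** 1. Replace the envelope with release of each assignment by the existing remote investigator, by telephone or message. Release should follow only after the patient's study code, signed consent, completed eligibility checklist and completed baseline evaluation have been registered irrevocably. Every allocated patient is then traceable and has the baseline that the analysis set requires.
2. Have the central program stratify by centre with randomly varying, undisclosed block sizes, pooling very small centres by a rule fixed before recruitment.
3. Name centre (or the pooled strata) as a factor in the analysis model. Stratifying without this would leave the standard error too large and forgo the gain.
4. If envelopes are kept, specify that they are sealed, opaque, sequentially numbered and logged.

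The cost is a change to the list-generation program and about a paragraph of protocol and analysis text. The 182 per arm stays as it is, and no extra patients or staff are needed. There are two downsides: the remote investigator must be reachable at enrolment, and blocking leaves slight predictability, which varying block sizes reduce but do not remove.

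### The plan permits the allocation envelope to be opened before the baseline SGRQ is completed, and then makes entry to the analysis set depend on that baseline

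*Combined protocol and SAP*

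**What the plan says.** All the relevant text is in section 3 (Methodology) of the combined protocol and SAP.

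- **Opening the envelope** (Sample size and sample procedure). It is "opened when the professional has confirmed that he complies with the selection criteria and the patient has signed the informed consent". These are the only two conditions.
- **The consent visit** (same paragraph). After first contact, "a visit will be scheduled to explain the study and to obtain the signed informed consent and the collection of data". The envelope's place within that visit is not given.
- **Timing of baseline** (text before Data analysis). "All the variables studied will be collected at baseline, prior to the intervention, and at 6, 12 and 24 months later". For controls, "a visit will be scheduled to obtain the same variables as the intervention group, on a first visit".
- **Instrument** (Variables). Quality of life is measured with "specific and standardized self-administered questionnaires", the SGRQ among them.
- **Analysis set** (Data analysis). The analysis is called intention to treat, and then: "All patients who signed their informed consent and who have completed the initial evaluation will be included in the analysis".
- **Analysis variable** (Data analysis). For each time point a variable is formed, "which is the difference between the result of SGRQ and the other dependent variables of interest in each cut and the initial value".
- **Masking** (Difficulties and limitations of the study). The patients' usual professionals can know the group. The team will try to keep masking for random allocation, evaluation of the main measures and statistical analysis, but no procedure is described.

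**The concern.** Allocation and the start of the intervention are different events. A baseline taken after the envelope is opened but before the first nurse session meets every timing rule in the plan. Two things would then be at stake.

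First, the patient would answer a subjective questionnaire already knowing the group. The initial SGRQ is subtracted from every later value. A reporting difference between arms that exists at baseline and has gone by follow-up therefore enters the estimated effect one for one. The planned check of baseline homogeneity could not tell such a difference from chance imbalance.

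Second, a patient could be randomised, learn the group, not complete the initial evaluation and be left out. That is an exclusion after randomisation. It could differ by arm, and it would not fit the intention-to-treat label.

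**Working it through.** **1. What the timing rules allow.**

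| Order | Envelope rule met? | Baseline rule met? | Consequence |
|---|---|---|---|
| Consent, baseline, envelope, intervention | Yes | Yes | Baseline cannot reflect allocation; completing it is an ordinary entry condition |
| Consent, envelope, baseline, intervention | Yes | Yes | Baseline may reflect allocation; non-completers are randomised and then excluded |

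Both orders comply with the text, which does not choose between them. The sentence on the control group describes scheduling a first visit for people already called controls, and can be read as the second order. The single visit for consent and data collection sits comfortably with the first.

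**2. The plan's own sample size.** Inputs from Sample size and sample procedure: difference 3.51, SD 11.33, two-sided alpha 0.05, power 80%, 10% loss.

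n per arm = 2 × [11.33 × (1.960 + 0.842) / 3.51]² = 163.6, so 164. Allowing for loss: 163.6 / 0.9 = 181.7, so 182. The stated figure reproduces and is not in question.

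**3. Illustration of a baseline shift.** The following are assumptions, not in the documents: a baseline to follow-up correlation ρ of 0.5 to 0.7, and a between-arm shift b in baseline SGRQ caused by knowing the group and absent at follow-up.

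SE of the difference in mean change = 11.33 × √(2(1 − ρ)) × √(2/164)

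- ρ = 0.5: 11.33 × 1.000 × 0.1104 = 1.25
- ρ = 0.7: 11.33 × 0.775 × 0.1104 = 0.97

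Type I error = P(|Z + b/SE| > 1.96)

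| Shift b (units) | b as share of 3.51 | ρ = 0.5 | ρ = 0.7 |
|---|---|---|---|
| 0 | 0% | 5.0% | 5.0% |
| 0.5 | 14% | 6.9% | 8.1% |
| 1.0 | 28% | 12.6% | 17.8% |

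The plan does not say whether 11.33 is the SD of a score or of a change. At ρ = 0.5 the two are equal, so that column serves both readings.

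A shift in the direction that hides a benefit costs power instead. With SE 1.25 and a true difference of 3.51, power falls from 80% to 67% (0.5 unit) or 52% (1 unit).

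If a fraction f of the shift persists at follow-up, the bias by this route is b × (1 − f). With f = 1 it is zero.

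**4. Illustration of the exclusions.** Assume 2%, 5% or 10% of randomised patients are dropped for an incomplete baseline, on top of the 10% loss. Evaluable patients per arm are 182 × 0.98 × 0.9 = 160.5, 182 × 0.95 × 0.9 = 155.6 and 182 × 0.90 × 0.9 = 147.4. Power is 79.3%, 78.0% and 75.8%. The loss of numbers is small; what matters is whether the exclusions differ by arm.

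**The case against.** The strongest reply is that the plan leaves the order open and does not state a wrong one. Data collection is already attached to the consent visit. Eligibility and consent can be read as minimum conditions for opening the envelope, and the team intends to keep masking at allocation and at evaluation. If every centre completes the initial evaluation first, both problems vanish together, because both rest on the same order. This stands, and it limits the conclusion. It does not remove the point: no visible sentence places baseline before the envelope, and an intention to mask cannot blind a patient who fills in a questionnaire after learning the group.

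The item on collection of data and sources of information has a title but no text in the copy reviewed. Text lost in conversion might settle the order, so the statement that no sentence does so covers the visible text only.

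The size of the effect is also open to challenge. Nothing in the documents supports a shift of 0.5 or 1 unit, its direction or the correlation. Patients would also know their group at 6, 12 and 24 months, so a reporting shift could persist and cancel. This too stands, and the figures are illustrative only.

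A reader might infer that baseline SGRQ values will be contaminated, that randomised patients will be dropped, or that the trial's type I error is 13-18%. The documents support none of these. They show only that the written rules do not prevent the first two, and the third depends wholly on assumed inputs.

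**Conclusion.** The point holds as a permitted risk. A centre following the written conditions literally could open the envelope before the self-administered SGRQ is completed, and could then lose randomised patients from a set described as intention to treat. In a multicentre trial, practice could also differ between centres.

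The possible bias cannot be sized from the documents. The range of about 7-8% (0.5 unit) to 13-18% (1 unit) for type I error assumes 164 per arm, SD 11.33, correlation 0.5 to 0.7 and a shift wholly gone by follow-up. No figure in the plan is wrong. The change is worth making because it alters two stated rules, closes both routes to bias and costs very little.

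**What to change.** 1. **Sample size and sample procedure:** add a third condition, that the envelope is opened only after the baseline questionnaires and the other baseline measures have been completed and recorded at the consent visit.
2. **Data analysis:** define the intention-to-treat set as all randomised patients, analysed in the group assigned.
3. **Data analysis:** state how a missing baseline is handled. Simply keeping such patients in is not enough, because the planned change score cannot be computed without an initial value. A likelihood-based repeated-measures model with baseline as one of the outcomes would serve, as would imputation. With the first change in place, wholly missing baselines should be rare.

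The cost is a sentence in the randomisation procedure, a revised definition of the analysis set, and slightly more analysis work for any missing baselines. Consent and data collection already share a visit, so no extra visit is needed, and 182 per group is unchanged.

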## **2. HYPOTHESIS AND OBJECTIVES**

Hypothesis: In patients with moderate to severe COPD, structured intervention in self-care is more effective than usual intervention in the main variables associated with the disease: quality of life, pulmonary function, exacerbations, hospital admissions, and primary care visits in a follow-up of 6, 12 and 24 months.

Overall objectives: To evaluate the impact of a comprehensive intervention to promote self-care and to improve the quality of life in people with Chronic Obstructive Pulmonary Disease (COPD) in Primary Care (PC).

Specific objectives: 1.- To describe the profile of patients with COPD in our area through the main sociodemographic characteristics (sex, age, level of studies), risk factors, COPD phenotypes, respiratory function, prognosis, pharmacological treatment, technique inhalation, exacerbations and hospital admissions, comorbidities, and quality of life.

2.-To assess using a clinical trial the effectiveness of a self-care program on different dimensions of clinical importance in COPD (degree of dyspnoea, prognosis, number of exacerbations, number of hospital admissions, degree of anxiety and depression).

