#### Additional procedures derived from the study

Group intervention: 4 to 6 visits will be scheduled with the reference nurse, 20 "in duration and separated 15 days.

Contents: Knowledge of the disease. Healthy lifestyle habits. Correct technique for the use of inhalers. Symptom control skills. Strategies for confronting the disease.

Specific contents: Behavioral change techniques, knowledge about COPD, adherence to the therapeutic plan (pharmacological and non-pharmacological), abandonment of the tobacco habit, alcoholic beverages, avoidance of environmental and working exposures, recommended vaccinations, inhalation techniques, knowledge about drugs used, basic respiratory exercises, energy saving techniques, relaxation techniques, recognition and performance of exacerbations, physical exercise enhancement, correct nutrition, sexuality.

The visits will be customized according to the clinical profile of the patient, the phenotype, the specific needs, their preferences and the stage of the change process in which he is found to be. All the sessions will be monitored by means of a specific track record where all activities / interventions will be collected, and the data collected (stage of the process of change, life habits: tobacco, diet, exercise, respiratory physiotherapy, inhalers ...). It will advise and facilitate attendance at the sessions of possible caregivers.

The behavioral components common to all the sessions will be: the setting of objectives, the motivational interview, providing feedback and behavioral cognitive therapy.

All learning will be based on educational material that will be provided to the patient: audiovisual, written educational material, links to web pages with useful and proven information (for example papsf ("Primary Health Care"), "the virtual nurse" or "caregiver" ) and, above all, the tutored practice of skills.

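### A one-year look-back for admissions at the 6-month visit includes months before randomisation, so the 6-month value is not comparable with the 12- and 24-month values

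*Combined protocol and SAP*

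**What the plan says.** Section 2 includes admissions among the main variables of the hypothesis: "quality of life, pulmonary function, exacerbations, hospital admissions, and primary care visits in a follow-up of 6, 12 and 24 months". In Section 3, under Variables, the only definition is "Hospital admissions in the last year (computerized medical history review". It is listed with the outcomes, ahead of the independent and confounding variables.

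The same section sets the schedule: "All the variables studied will be collected at baseline, prior to the intervention, and at 6, 12 and 24 months later", in both arms. No visit has its own look-back. Controls give the same data "as the intervention group, on a first visit, and at 6, 12 and 24 months".

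The data analysis text dates the follow-up differently, with a change variable for each "measurement time (baseline, 6 months post-intervention and 12 and 24 months". That variable is the difference between the SGRQ and "the other dependent variables of interest in each cut and the initial value, for each individual". Then: "An analysis of the variance of repeated measures (ANOVA) will be performed to evaluate the differences in time of dependent variables".

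The section on additional procedures gives the length of the intervention: "4 to 6 visits will be scheduled with the reference nurse", 15 days apart.

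**The concern.** Allocation follows consent, so randomisation falls at about the baseline visit. A year counted back from month 6 then covers roughly six months in which no treatment effect is possible. A year counted back from month 12 or month 24 is wholly post-randomisation. The 6-month and 12-month values also share months 0 to 6.

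All three values carry the same label, admissions in one year, and enter the same analysis over time. A reader who takes them as like for like would see a smaller effect at 6 months than at 12, even if the intervention reduced the admission rate by the same amount throughout, and could report that as a benefit that builds up.

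The two ways of dating the 6-month visit add to the problem. Control patients have no end of intervention, so the post-intervention origin cannot serve both arms.

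**Working it through.** **The plan's own figure.** The only calculated figure is the SGRQ sample size (Section 3): difference 3.51, SD 11.33, two-sided alpha 0.05, power 0.80, loss 10%. 2 × (11.33 × 2.8016 / 3.51)² = 163.6 per arm, and 163.6 / 0.9 = 181.7. This agrees with the stated 182. About 164 per arm would be analysed.

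**Exposed share of the 6-month look-back.** Inputs: a 12-month look-back, the visit schedule, and 4 to 6 visits 15 days apart (3 to 5 gaps, so 45 to 75 days). The first session is assumed to follow randomisation at once, because the documents give no interval.

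- From baseline: 6 exposed months, 6/12 = 50%.
- Six months after the last of 4 visits: 6 + 45/30.44 = 7.48 exposed months, 7.48/12 = 62%; 4.52 months precede randomisation.
- Six months after the last of 6 visits: 6 + 75/30.44 = 8.46 exposed months, 8.46/12 = 71%; 3.54 months precede randomisation.

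With control rate λ per year and an immediate, constant rate ratio RR, the expected 12-month difference is λ(1 − RR) and the 6-month difference is (exposed months/12) × λ(1 − RR). The rate cancels, so these shares need no assumed admission rate on the additive scale of the plan. The 12-month difference is 12/6 = 2.0 times the 6-month one, or 12/7.48 = 1.60 and 12/8.46 = 1.42. In simulation at an assumed 0.5 admissions per year and RR 0.7, the mean differences in change were −0.075 at 6 months, −0.152 at 12 and −0.151 at 24.

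**What the planned change score estimates.** With baseline as origin, the 6-month value covers (−6 to +6) and the baseline value (−12 to 0). Months −6 to 0 cancel, leaving (0 to 6) − (−12 to −6). By randomisation the second term has the same expectation in both arms, so the group difference is unbiased for the difference in admissions in months 0 to 6.

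**Precision, a separate matter.** Let h be half the yearly rate and t the variance of patient-level frailty; a count with mean m has variance m + t·m², and counts with means a and b have covariance t·a·b. Compare the planned change with the 0–6 month count adjusted for the 12-month baseline count, variances summed over arms, at RR 0.7.

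- Poisson (t = 0): change (3 + RR)h, adjusted count (1 + RR)h; ratio 3.7/1.7 = 2.18 at any rate.
- 1.0 per year, t = 4: change (1.5 + 1.5 − 2.0) + (0.84 + 1.5 − 1.4) = 1.94; adjusted count 1.5 + 0.84 − (2.0 + 1.4)²/10 = 1.184; ratio 1.64.

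Over assumed rates of 0.12 to 1.0 per year and t from 0 to 4, the ratio lies between 1.64 and 2.18. The Poisson ratio at month 12 is also 2.18, so the cause is the subtraction, not the look-back.

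**Chance of a misleading test.** The documents give no admission rate for this sample. Section 1 reports that more than 12% of patients are admitted each year; at 12% this implies −ln 0.88 = 0.128 per year (Poisson), or 0.167 with t = 4. In 6,000 simulated trials per setting with RR 0.7, 164 per arm and a constant effect, the 6-to-12-month contrast was significant in 8.1% to 8.6% at 0.13 to 0.17 per year, about 11% at 0.25, about 17% at 0.5 and 28% to 29% at 1.0.

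**The case against.** The strongest reply is that nothing is biased. Six months of exposure avoids half as many admissions as twelve, whatever the look-back, and the change score recovers exactly that. This stands. A reader might infer that the 6-month comparison is invalid, or that chance imbalance in the pre-randomisation months contaminates it; the planned subtraction rules out both. What remains is comparability: the value is defined as a yearly count and analysed over time beside fully exposed years.

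A reader might also infer that a true rate ratio of 0.7 would be reported as 0.85 at 6 months. The arithmetic is right (0.5 + 0.5 × 0.7), but the plan specifies differences and ANOVA, not a rate ratio.

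An immediate effect is doubtful for education delivered over weeks. If it began only after 75 days (2.46 months), the 6-month difference would be 3.54/9.54 = 37% of the 12-month one. With correct windows, months 0–6 would still show only 3.54/6 = 59% of the full rate effect. So a rise could be real, and the fix would not remove it; the fix stops the look-back from adding an artificial one.

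The loss of precision should not be charged to the look-back. Against an unadjusted 0–6 month count the variance ratio runs from 2.18 down to 0.83, so the gain depends on using baseline as a covariate.

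Finally, the heading on data collection and sources has no content in the available text. A visit-specific window given there would settle the point.

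**Conclusion.** The point holds in a limited form. As written, the 6-month admissions value includes about 6 months before randomisation, or about 3.5 to 4.5 on the post-intervention timing. As a one-year outcome it is expected to show 50% (62% to 71%) of the 12-month difference. That share assumes an immediate, constant effect and no gap before the first session.

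The harm is a 6-month estimate that is easily misread and a time comparison that mixes unlike years. A formally significant false trend is unlikely at rates near the Section 1 figure. Only the 6-month time point of an outcome on which the trial was not sized is affected; the 12- and 24-month look-backs lie wholly after randomisation. The variance ratio of about 1.6 to 2.2 is a separate cost of subtracting baseline and rests on assumed rates, dispersion and RR 0.7. The plan should be amended on this point, but the SGRQ analysis is not threatened.

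**What to change.** - Time all visits from randomisation in both arms, and reconcile the post-intervention wording in the data analysis text with this.
- From the record review already planned, abstract admission dates and count admissions in months 0–6, 6–12 and 12–24.
- Compare groups as rates per person-time, with 95% CIs. Non-overlapping windows alone are not enough: under a constant effect, raw counts over 6 and 12 months would still differ about twofold.
- Use the count in the 12 months before randomisation as a covariate and do not subtract it. Change the window and the subtraction together: under Poisson with RR 0.7, a 0–6 month count minus a full baseline year has (5 + 0.7)/(1 + 0.7) = 3.35 times the variance of the 0–6 month count.

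The count model is a matter of choice; negative binomial, or Poisson with robust errors, each with log follow-up time as offset, would serve. A 0–24 month total may be added.

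The cost is revised wording and slight extra work to abstract dates. The 182 per group is unaffected.
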